7. Evaluations of exclusion
8. High status occupation expectations
9. Positive trait attributions*
10. Expectations of inclusivity
11. Math and science competency beliefs

**Indicates mean composite variable*

Measures also included in analyses, depending on model selection:

- Participant race/ethnicity (parent report)
- Gender (parent report)
- Grade level (3, 4, 5)
- Pretest measure for the respective outcome model was included as a control in each model
- School

Analysis Procedure

We first examined ICCs for classroom level and school level to determine if multilevel modeling was needed and conducted model comparisons to determine if classroom, school, and sex should be included as fixed effects. We selected models for each outcome variable based on lowest AIC and BIC.

We also conducted exploratory factor analyses on reported contact measures, desire to play measures, and evaluations of exclusion to determine if creating composite measures was most appropriate for analysis.

For all models, we included school, classroom, and gender if model comparisons indicate, using the model with lowest AIC and BIC for a given outcome variable.

We conducted multiple regression linear regression for all **composite variables**, using the base model:

```
lm(posttest DV ~ pretest DV + treatment*grade + race-ethnicity)
```

For all individual items for **reported contact, desire to play, evaluations of exclusion, expectations of inclusivity, and math/science competency beliefs**, we conducted ordinal logistic regression using the base model:

```
polr(posttest DV ~ pretest DV + treatment*grade + race-ethnicity)
```

For **high status occupation expectations**, we examined outcome distributions to determine if it is appropriate to collapse response options by stimuli gender and/or race. We conducted multinomial logistic regression using the base model:

```
multinom(posttest DV ~ pretest DV + treatment*grade + race-ethnicity)
```

Exploratory Analyses

For the above models, we tested the model removing the grade*treatment interaction, if it is not significant, to isolate the treatment effect. We also tested interactions of treatment*grade and treatment*gender to determine if the treatment was more effective for certain demographic groups.

Inference criteria

We considered predictors significant at a *p*-value of .05. We used Bonferroni adjustment for multiple groups pairwise comparisons.

Data exclusion

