Children who could not independently complete the survey and had no trained adult available to assist them complete the pre-test and/or post-test were excluded from the sample and the subsequent analyses.

Missing data (optional)

We conducted imputations using predictive mean matching to address missing values. We imputed 30 datasets using the “mice” package in R. Demographic variables (grade, classroom, condition, gender, and school) were included as predictors, while pretest scores, posttest scores, and race were included as both predictors and imputed values. All analyses were conducted on the 30 imputed datasets individually and the pooled results were reported.

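### The SAP does not say that one model per outcome was held fixed across the 30 imputed datasets, so the pooled treatment coefficient may not have a single meaning

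*SAP*

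**What the plan says.** The SAP section *Missing data (optional)* describes multiple imputation by predictive mean matching: "We imputed 30 datasets using the" R package mice. It adds that "pretest scores, posttest scores, and race were included as both predictors and imputed values", and on analysis it says: "All analyses were conducted on the 30 imputed datasets individually and the pooled results were reported".

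The model form is data-driven in several places. Under *Analysis Procedure*, the choice between single-level and multilevel models comes from intraclass correlations ("We first examined ICCs for classroom level and school level to determine if multilevel modeling was needed"). Classroom, school and sex or gender enter according to model comparison: "We selected models for each outcome variable based on lowest AIC and BIC", repeated as "using the model with lowest AIC and BIC for a given outcome variable". Factor analysis is used "to determine if creating composite measures was most appropriate for analysis". All three base models (`lm`, `polr`, `multinom`) contain treatment by grade. Under *Exploratory Analyses*, "we tested the model removing the grade*treatment interaction, if it is not significant", with the stated aim of isolating the treatment effect. The significance level under *Inference criteria* is .05.

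The SAP does not say which data these choices were made on (observed, one imputed dataset, each dataset, or all combined), whether significance of the interaction refers to the pooled test, or what follows if datasets, or AIC and BIC, disagree.

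**The concern.** Rubin's rules average an estimate over imputed datasets on the premise that each dataset estimates the same parameter. Pretest, posttest and race are imputed, so AIC, BIC and the interaction p-value all vary from one dataset to the next. If the model is allowed to vary with them, the average may have no single target.

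The interaction matters most. With it in the model and grade coded as a factor in R's default way, the treatment coefficient is the effect in the reference grade. Without it, the coefficient is an average effect over grades. That coefficient bears on every hypothesis under 1.1. In the ordinal and multinomial models a milder version arises with covariates: adding or dropping a prognostic covariate changes the scale of the treatment coefficient even under randomisation.

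At stake is whether a reported pooled estimate and p-value belong to one definable model, and whether the between-imputation variance reflects missing data alone.

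**Working it through.** The plan gives no figure on this point, so there is nothing to reproduce. The check is algebra plus an illustrative simulation.

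**Inputs from the documents.** 30 imputations, .05 level, imputed pretest, posttest and race (SAP); 885 children and three grades (Protocol, *Settings and Participants*).

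**Inputs assumed.** Missing posttests 2% to 20%; treatment effect 0.15 SD; grade-by-treatment slope 0, 0.10 or 0.15 SD per grade; gender effect 0.1 SD; six schools with school SD 0.1; individual randomisation; no classroom effect; a linear outcome; a main-effects imputation model with 5 donors.

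**Step 1: what each coefficient means.** With slope 0.15, the effect in grade g is 0.15 + 0.15 × (g − 4).
- Grades 3, 4, 5: 0, 0.15, 0.30.
- Model with interaction, grade 3 as reference: treatment coefficient targets 0.
- Model without interaction, equal grades: targets (0 + 0.15 + 0.30)/3 = 0.15.
- If grade were instead entered as the uncentred number 3, 4, 5, the first coefficient would target grade 0: 0.15 + 0.15 × (0 − 4) = −0.45. The SAP does not state the coding.

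**Step 2: what pooling would do.** The pooled estimate is the mean over 30 datasets. If k datasets keep the interaction, it targets (k/30) × 0 + ((30 − k)/30) × 0.15. At k = 15 this is 0.075, which is neither quantity.

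**Step 3: how often datasets would disagree if each chose for itself.** There were 300 runs per setting, so the simulation error of a share is at most √(0.25/300) = 0.029. A run counts as disagreeing if even one of the 30 datasets differs. Ranges are over the three slopes.

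| Missing posttests | Keep/drop differs | AIC set differs | BIC set differs |
|---|---|---|---|
| 2% | 8–24% | 36–41% | 19–20% |
| 5% | 11–32% | 51–59% | 24–29% |
| 10% | 18–46% | 67–71% | 41–45% |
| 20% | 21–62% | 81–86% | 61–66% |

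Keep/drop used a 2-df F test at .05. AIC and BIC chose among models with or without gender and school. The two criteria disagreed with each other in at least one dataset in 89% to 99.7% of runs.

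**Step 4: consequence in the disagreeing runs.** At 10% missing and slope 0.15, the mean pooled treatment coefficient was 0.138 with the main-effects model fixed, −0.009 with the interaction model fixed, and 0.070 mixed. At slope 0 the three were close (0.146, 0.135, 0.136), so the mean is distorted only when a real interaction exists. Over all settings, the between-imputation variance was about 4 to 69 times that of the fixed main-effects model. The ratio is largest at 2% missing, where that component is smallest; it is not a ratio of standard errors.

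**Step 5: covariates.** A second simulation (150 outcomes per level, 44 classes and six schools assumed) gave AIC disagreement of 45%, 72% and 86%, and BIC 17%, 29% and 52%, at 5%, 10% and 20% missing. Over 600 datasets, having school in rather than out moved the treatment estimate by about 0.2 to 0.4 of its standard error, and gender by about 0.06. These are full in-versus-out shifts; a mixture moves the pooled value less.

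Neither simulation let classroom enter or leave, and the keep/drop results cover the linear model only.

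**The case against.** A reader might infer that the SAP prescribes selection separately in each imputed dataset, and that the datasets will therefore end in different models. The text does not support that. It twice makes the outcome the unit of selection, which points to one model per outcome, and it places the intraclass correlations and model comparisons first. Since AIC and BIC have no standard pooling rule, the sentence about analysing and pooling 30 datasets reads more naturally as covering the fitted models than the choice among them.

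The interaction step is also open to a benign reading. Treatment by grade is fixed in every base model, and the reduced model is listed as exploratory, so it may be an extra fit rather than a replacement. With pooled results reported, non-significance may well mean the pooled test. On those readings nothing is mixed.

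Nor would disagreement be certain under per-dataset selection: in the second simulation at 5% missing, all 30 datasets agreed for 55% of outcomes under AIC and 83% under BIC. The effect of covariate switching alone is modest.

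All of this stands. What remains is that the SAP states neither safeguard, and has no rule for AIC and BIC pointing to different models. The benign readings are plausible, but they have to be supplied by the reader.

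**Conclusion.** The point holds as a gap in specification with a potentially serious consequence, not as a demonstrated error. The SAP combines pooling over 30 datasets with data-driven model choice and does not say that the model was held constant or that the interaction was judged on the pooled test. If the choices were made per dataset, the interaction rule could yield a pooled coefficient that is neither the reference-grade nor the average effect. Covariate choice would shift linear estimates by a fraction of a standard error.

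The documents do not show that mixing occurred. The percentages are conditional on per-dataset selection and on assumed missingness, school effects and interaction size; since no missing-data rate is given, they show that the problem is realistic, not how large it was. The scale change in the ordinal and multinomial models is an argument of principle, with no figure attached.

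**What to change.** 1. Replace the AIC/BIC choice of school and gender with one covariate set for every outcome: pretest, grade, race-ethnicity, gender and school. School belongs in because the Protocol's opening paragraph describes randomisation within schools. Fit the same model in all 30 datasets. This also removes the need for a rule when AIC and BIC disagree.
2. Decide on grade by treatment once per outcome, from a pooled multi-parameter Wald test of all its interaction terms, and apply the decision to all 30 datasets. State how grade is coded and which effect the reported treatment coefficient represents.
3. Treat classroom clustering as a separate decision, made once per outcome and applied to all 30 datasets. The fixed covariate set does not settle it, and it matters because teachers deliver the program in classrooms.

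With these in place, mixing cannot occur by construction.

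**Cost.** SAP wording and re-pooling. In the linear models, gender takes 1 degree of freedom and school one fewer than the number of schools; with the six schools assumed above, that is 1 + 5 = 6 in 885 children. The multinomial models pay this once per non-reference category. If one model per outcome was already fitted throughout, the interaction and clustering parts may need only a sentence each, but outcomes whose model lacked school or gender would still be refitted.
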